11.2.2 Events Not Classified as an SAE in the MODULATE trial

The following events will not be recorded as SAEs within this study:

Hospitalisation for:

- Routine treatment or monitoring of the studied indication not associated with any deterioration in condition;
- Treatment that was elective or pre-planned, for a pre-existing condition not associated with any deterioration in condition;
- Admission to hospital or other institution for general care, not associated with any deterioration in condition;
- Treatment on an emergency, outpatient basis for an event not fulfilling any of the definitions for serious, as given above, and not resulting in hospital admission.

11. 2.3 Adverse Events of Special Interest

Constipation

Collected by participant self-report on the 8-week and 6-month questionnaires.

Flare of Disease Activity

Any participant suspected to have a flare of disease activity must undergo immediate investigation as follows:

- Blood for CRP (normal result<5mg/L)
- Stool for FC (normal result<250mcg/g)

If the CRP and/or the FC results are abnormal (CRP \geq 5mg/L, FC \geq 250mcg/g), the patient will have a limited flexible sigmoidoscopy to assess for evidence of mucosal inflammation. If both CRP and FC are normal it is at the treating physician's discretion, in consultation with the

participant, to decide whether a limited flexible sigmoidoscopy is still required. If flare of disease activity is confirmed after sigmoidoscopy (endoscopic Mayo score >1), this is classed as an AE of special interest and will be expedited to the CTRU for review on the Flare CRF within 24 hours of the site confirming the event. The patient's trial treatment will be discontinued, and they will be referred back urgently to their responsible gastroenterologist for appropriate management.

Self-harm or Suicide

Any reported form of self-harm, or suicide, will be treated as an IME and reported to the CTRU within 24 hours of the site becoming aware of the event on an SAE form.

11.3 MODULATE Reporting Requirements

All SAEs, SARs, and SUSARs will be collected from time of consent up to 7 days after the last dose of IMP. All SAEs and SUSARs should be reported to the CTRU within 24 hours of the site becoming aware of the event. If sites become aware of any SARs or SUSARs occurring after this active monitoring period, these must still be reported in an expedited manner **up to 90 days after the end of trial**.

The following details will be collected for each SAE:

- Place the SAE started;
- Full details in medical terms with a diagnosis, if possible;
- Duration (date of onset and date of resolution);
- The arm that the patient was randomised to on study;
- Seriousness criteria;
- Causality, in the opinion of the PI or delegate;
- Local opinion on expectedness as defined by the trial supplied RSI, if applicable;
- Action taken with regard to study medication, if applicable;
- Outcome.

In addition to the above the following details will be collected for each SUSAR:

- Relevant medical history;
- Concomitant medications;
- Treatment for SUSAR;
- Relevant diagnostic tests.

To report an SAE or SUSAR please complete an SAE/SUSAR CRF in as much detail as possible, and ensure that the PI or delegate has reviewed the event for causality and expectedness, and has signed the form.

All SAEs and SUSARs will be reviewed by the CI, or designated representative, to confirm causality and expectedness. In the event of a SUSAR, the CTRU will notify the Medicines and Healthcare products Regulatory Agency (MHRA), research ethics committee (REC), and Sponsors office. SUSARS will be reported to the MHRA and REC within the required expedited reporting timelines.

SAE/SUSAR CRF's should be faxed to the CTRU on [name]

All SAEs/SUSARs will be followed-up until resolution or a final outcome has been reached. All follow-up information should be faxed/emailed to the CTRU as soon as it is available.

Please retain the original SAE/SUSAR CRF until the CTRU confirm all information is complete and any resulting queries have been resolved. At this point the original should be posted to the CTRU in real time and a copy retained in the site file.

 Table 1 Summary of safety reporting requirements

Event	Report on trial CRF					
	Drug arms	Non drug arms				
AE	\checkmark	\checkmark				
AE of special interest	\checkmark	\checkmark				
AR	✓	×				
SAE	✓	\checkmark				
SAR	✓	×				
SUSAR	✓	×				
RUSAE	×	\checkmark				

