3.3 Secondary Objectives

Our secondary objectives are to answer the following questions at both 8 weeks and 6 months:

- 1. What is the effect of the active treatments, compared with a control of standard firstline dietary advice, in terms of:
 - a. Improvement in discomfort from (i) loose stools, (ii) diarrhoea, (iii) urgency, and (iv) abdominal pain, each assessed via the GSRS-IBS [26]?
 - b. Markers of disease activity, including escalation of medical therapy, need for surgery, faecal calprotectin (FC), and C-reactive protein (CRP)?
 - c. Mood, via the hospital anxiety and depression scale (HADS) [28]?
- 2. What is the tolerability and safety of the active treatments, compared with a control of standard first-line dietary advice?
- 3. What is the adherence to each of the active treatments, compared with a control of standard first-line dietary advice?

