8.7 Discontinuation of Study Treatment

In line with usual clinical care, cessation or alteration of regimens at any time will be at the discretion of attending clinicians, or the participants themselves. All participants who discontinue from treatment, or who are prescribed alternative treatment, will still attend for follow-up assessments and complete questionnaires, unless they withdraw from the trial (see section 10). Data pertaining to safety will continue to be collected for regulatory reporting purposes and will be included in any safety analysis. The reason for discontinuing study medication will be recorded. Reasons for study treatment discontinuation include:

- Patient decision;
- Severe non-compliance to this protocol as judged by the investigator;
- Safety, including allergic reaction to IMP;
- If the investigator considers that a patient's health will be compromised due to AEs or concomitant illnesses that develop after entering the study;
- Receipt of a restricted concomitant medication after entering the study;
- Pregnancy;
- Overdose;
- Suicidal ideation;
- Flare of disease activity.

Once study medication is permanently discontinued it cannot be restarted as part of the study. Patients should return all unused IMP on cessation of trial treatment. If a participant withdraws from treatment, a Treatment Discontinuation CRF should be completed by the site.

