9.2.2.1.2 Data Collection from Medical notes

The following data will be collected from the medical notes and recorded on the CRF:

- Confirmed flare of disease activity;
- Any requirement for escalation of UC-related medical therapy;
- Need for surgery.
- Collection of SAEs/SARs/SUSARs/RUSAEs experienced since randomisation;

9.2.2.2 6-month Face-to Face visit- All Participants 9.2.2.2.1 Patient Reported Questionnaires

Participants will self-complete a questionnaire booklet at 6 months post-randomisation. Participants completing questionnaires online will be sent the questionnaire via text message and/or email. Participants completing questionnaires on paper will be sent the questionnaire via post; the research nurse will contact the participants at 6 months to remind them to complete the booklets and return them. They will be sent an SMS reminder and an email to prompt completion. If the questionnaire has not been completed by the time the participant attends the 6-month face-to-face visit, they will be asked to complete it at the visit on paper.

Questionnaires will include:

- GSRS-IBS [26];
- IBD-Q [27];
- Tolerability;
- HADS [28];
- Need for either escalation of medical therapy for UC or surgery;
- CNAQ [34] (low FODMAP arm only).

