11.2 MODULATE Operational Definitions

The safety profile of all the IMPs in MODULATE are well known. It is therefore not the intention of this study to collect all AEs. The occurrence of reportable AEs will be self-reported by the participant on the participant questionnaires at 8 weeks and 6 months for patients in all arms. Only the confirmation of occurrence and corresponding severity (mild-noticeable but not preventing normal activities, moderate-restricting some activities, severe- preventing any activities) will be recorded. SAEs, SARs, and SUSARs will be collected for the duration of the trial. The following AEs will be collected:

- Constipation;
- Abdominal pain / bloating (as part of the condition being treated);
- Headache;
- Nausea;
- Vomiting;
- Rectal bleeding:
- Dizziness

- Drowsiness
- Dry mouth
- Insomnia

11.2.1 Adverse Events / Adverse Reactions and Serious Adverse Events / Serious Adverse Reactions

For general definitions of AEs, ARs, SAEs and SARs, please see section 11.1 above.

When determining whether a SAE or SAR is expected or not, please refer to section 4.8 of the current RSI SPC, for the relevant IMP which is provided in the Investigator Site File.

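### Section 11.3 ends SAE collection 7 days after the last IMP dose, which contradicts 11.2, conflicts with 8.7 and 9.2, and sets no end point for the two arms without IMP

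*Protocol*

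**What the plan says.** Protocol 11.3 (MODULATE Reporting Requirements) sets the window: "All SAEs, SARs, and SUSARs will be collected from time of consent up to 7 days after the last dose of IMP". It treats this span as the active monitoring period and then adds: "If sites become aware of any SARs or SUSARs occurring after this active monitoring period, these must still be reported in an expedited manner". This later duty lapses 90 days past the close of the trial. Unrelated SAEs are not in that later rule.

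Other parts of the protocol read differently:

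- **11.2 (Operational Definitions):** "SAEs, SARs, and SUSARs will be collected for the duration of the trial".
- **8.7 (Discontinuation of Study Treatment):** participants who stop treatment "will still attend for follow-up assessments and complete questionnaires, unless they withdraw from the trial (see section 10"). On safety data after stopping, the same section says: "Data pertaining to safety will continue to be collected for regulatory reporting purposes and will be included in any safety analysis".
- **9.2.2.1.2 (8-week data from medical notes, all participants):** "Collection of SAEs/SARs/SUSARs/RUSAEs experienced since randomisation".
- **9.2.2.2.2 (6-month visit, all participants):** an SAE check is listed.
- **Table 1 (in 11.3):** SAEs are reported in both drug and non-drug arms.
- **Appendix 5:** control has SAE checks at week 8 and month 6. The low FODMAP arm has adverse event checks from medical notes at week 1, week 8 and month 6.

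The secondary objectives (3.3) ask: "What is the tolerability and safety of the active treatments, compared with a control of standard first-line dietary advice". Section 13.3.9 plans descriptive safety statistics by arm.

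**The concern.** The 11.3 window depends on how long a participant takes IMP. A drug-arm participant who stops early leaves the window a week later. A control or low FODMAP participant has no last dose, so the sentence gives no end point, and the assessments for those arms run to month 6.

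Stopping is also not random with respect to harm. The reasons listed in 8.7 include safety, adverse events, overdose and flare. Under 11.2.3, after a confirmed flare the participant's "trial treatment will be discontinued, and they will be referred back urgently to their responsible gastroenterologist". On a literal reading of 11.3, a hospital admission more than 7 days after that stop would be an SAE in control. In a drug arm it would not be collected unless judged related to the drug.

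At stake is the by-arm SAE summary, which serves the stated comparison with control and which the DMEC also sees. Raw counts over unequal windows can mislead even when no test is planned.

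**Working it through.** The protocol gives no SAE rate, no expected SAE count and no distribution of stopping times, so there is no stated figure to reproduce. The check has two parts.

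**1. The passages applied to one case.** Suppose a participant stops a study drug at week 6 and is admitted to hospital at week 20 for something judged unrelated. The research nurse learns of it at the 6-month visit.

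- Under 11.3 the window closed at week 7. The event is not a SAR or SUSAR, so the late rule does not bring it back. Not collected.
- Under 11.2 the trial is still running. Collected.
- Under 8.7 safety data continue and enter the safety analysis, but neither an end date nor the event types are given. This points to collection without settling it.
- Under 9.2.2.2.2 the nurse performs an SAE check, but the section does not say which late events are reportable.
- The same admission in a control participant has no 11.3 cut-off and is found at the month 6 check. Collected.

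Nothing in the protocol says which section prevails.

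**2. Size if 11.3 alone governed.** Inputs:

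- Treatment lasts 6 months (trial summary), taken as 26 weeks or 182 days.
- The lag is 7 days (11.3).
- The proportion stopping, w, is 20% or 40%. These are the green and amber limits for treatment drop-out in 4.4, used as illustrative values and not as expected rates.
- Stopping times are assumed.

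Share of arm time observed = (1 − w) + w × mean[min(182, t + 7)] / 182, where t is the stopping day.

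Uniform stopping in round figures: the mean stop is week 13, plus 1 week of lag, which leaves 12 of 26 weeks unobserved.

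- w = 20%: 0.20 × 12/26 = 9.2% lost.
- w = 40%: 0.40 × 12/26 = 18.5% lost.

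The formula in days gives the same result: the mean window for those who stop is 97.9 days, so 90.8% and 81.5% of arm time is observed.

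| Stopping time (assumed) | Days observed per discontinuer | Lost at w = 20% | Lost at w = 40% |
|---|---|---|---|
| All at day 21 | 28 of 182 | 16.9% | 33.8% |
| All at day 56 | 63 of 182 | 13.1% | 26.2% |
| Uniform over 182 days | 97.9 of 182 (mean) | 9.2% | 18.5% |

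With a constant SAE rate, SAEs in that arm would be under-counted by about the same percentages, with no loss in an arm followed to month 6.

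Under 11.2, 8.7 and 9.2, a participant who stops treatment but stays in follow-up contributes all 182 days, so the loss is 0%.

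**The case against.** The strongest reply is that the imbalance appears only if the sections are read asymmetrically. Control is followed to 6 months because of section 9, and the same section 9 checks apply to drug-arm discontinuers. Section 8.7 deals with discontinuers directly and keeps both their follow-up and their safety data. Read as a whole, the protocol probably intends collection to month 6 in every arm. This stands, and it makes the bias conditional.

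Further points that stand:

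- Confirmed flares, escalation of UC therapy and need for surgery are recorded at 8 weeks and 6 months in all arms, with no last-dose cut-off. In the flare example the flare itself is captured. What could be missing is the SAE record of a later admission.
- A reader might infer that unequal windows distort the choice of arms for phase 3. The documents give little support. Safety enters only if more than two arms qualify (13.3.6), the analysis is timed to 8-week follow-up (13.3.2), and the 8-week collection runs from randomisation for everyone.
- A reader might infer that the drug arms must look safer overall. That is not established. They have extra SAE enquiries at week 1, week 3 and month 3 that control lacks, which could raise ascertainment.
- Some reasons for stopping, such as patient decision or pregnancy, need not reflect harm from treatment.

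What the reply does not remove is the contradiction. Section 11.3 is the operative reporting section, and its late-event rule shows that the cut-off has consequences. Sections 8.7, 9.2 and Table 1 do not say that unrelated SAEs after the cut-off are reportable.

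**Conclusion.** The protocol contradicts itself on how long SAEs are collected. Section 11.3 stops at 7 days after the last IMP dose, 11.2 runs for the duration of the trial, and 8.7 and 9.2 fit 11.2 better than 11.3. The 11.3 sentence also leaves the control and low FODMAP arms without an end point.

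A site that follows 11.3 literally would omit unrelated SAEs in drug-arm discontinuers but not in control, and the by-arm summary would then rest on unequal windows. The illustrative loss of about 9% to 18% of a drug arm's observation time (17% to 34% if all stopping occurred at day 21) requires that 11.3 override the other sections and that the assumed drop-out and stopping times apply. If the other sections govern, the loss is 0% for those who stay in follow-up.

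It would go too far to say that the planned safety comparison is biased, or that no SAE window exists for control or diet. Section 11.2, the all-participant checks, Table 1 and Appendix 5 provide for SAE or adverse event collection in those arms. The point is still worth correcting, because sites can follow the two rules differently and the correction is cheap.

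**What to change.** Reconcile 11.3 with 11.2, 8.7 and 9.2 by stating one SAE collection period for all five arms: from consent to the participant's 6-month visit, or to 7 days after the last dose if that is later, whether or not treatment has stopped. Use the same sentence in 11.2 and 11.3, and refer to it from 8.7 and 9.2.

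Keep the start at consent, so that events before randomisation are still collected. Keep the existing rule for SARs and SUSARs that come to light afterwards. Base the between-arm SAE summary in 13.3.9 on the common period from randomisation to 6 months.

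The cost is protocol wording and a few more SAE forms from participants who stop early, who already attend the 8-week and 6-month assessments. Treatment and clinical management do not change.

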11.4 Responsibilities

Principal Investigator:

Activities marked with an asterisk (*) must be performed by a medically-trained doctor

• Checking for AEs and ARs when participants attend for treatment / follow-up;

- Using medical judgement in assigning seriousness, causality, and expectedness using the RSI approved for the trial*;
- Ensuring that all SAEs and SARs (including SUSARs) are recorded and reported to the CTRU within 24 hours of becoming aware of the event, and providing further followup information as soon as available. Ensuring that SAEs and SARs (including SUSARs) are chased with CTRU if a record of receipt is not received within 2 working days of initial reporting;

Ensuring that AEs and ARs are recorded and reported to the CTRU in line with the requirements of the protocol.

CI:

- Clinical oversight of the safety of participants participating in the trial, including an ongoing review of the risk / benefit;
- Using medical judgement in assigning seriousness, causality, and expectedness of SAEs where it has not been possible to obtain local medical assessment (this can be delegated to a clinical co-investigator);
- Immediate review of all SUSARs;
- Review of specific SAEs and SARs in accordance with the trial risk assessment and protocol as detailed in the Trial Monitoring Plan;
- Assigning Medical Dictionary for Regulatory Activities or Body System coding to all SAEs and SARs;
- Preparing the clinical sections and final sign off of the Development Safety Update Report (DSUR).

CTRU:

- Central data collection and verification of SAEs, SARs, and SUSARs according to the trial protocol onto a MACRO database;
- Reporting safety information to the CI, delegate, or independent clinical reviewer for the ongoing assessment of the risk / benefit according to the Trial Monitoring Plan;
- Reporting safety information to the independent oversight committees identified for the trial (Data Monitoring and Ethics Committee (DMEC) and / or TSC) according to the Trial Monitoring Plan;
- Expedited reporting of SUSARs to the competent authority (MHRA in UK), main REC, and Sponsor within required timelines;
- Notifying investigators of SUSARs that occur within the trial;
- Checking for (annually) and notifying PIs of updates to the RSI for the trial;
- Preparing standard tables and other relevant information for the DSUR in collaboration with the CI, and ensuring timely submission to the MHRA and Main REC.

Trial Steering Committee:

The TSC, with an independent chair, will provide overall supervision of the trial, in particular trial progress, adherence to protocol, participant safety, and consideration of new information. It will include an independent chair and not less than two other independent members. The CI

and other members of the TMG will attend the TSC meetings and present and report progress. The committee will meet annually as a minimum.

Data Monitoring and Ethics Committee:

The DMEC will review the safety and ethics of the trial by reviewing interim data during recruitment and treatment beyond the end of recruitment. The DMEC will meet or communicate via teleconference approximately annually as well as reviewing unblinded safety data at least 6-monthly. The subsequent frequency of review will be determined by the committee members. After each annual review, the DMEC will make their recommendations to the TSC about the continuation of the trial.

Trial Management Group

The TMG, comprising the CI, CTRU team, and co-investigators will be assigned responsibility for the clinical set-up, on-going management, and promotion of the trial, as well as the interpretation of results. Specifically the TMG will be responsible for:

- Protocol completion;
- CRF development;
- Obtaining approval from the main REC and supporting applications for site specific assessments;
- Completing cost estimates and project initiation;
- Appointing and facilitating the TSC and DMEC;
- Reporting of SAEs to relevant parties;
- Monitoring of screening, recruitment, treatment, and follow-up procedures;
- Auditing consent procedures, data collection, trial end-point validation, and database development.

11.5 Pregnancies

All pregnancies and suspected pregnancies in female participants should be reported to CTRU within 24 hours of the PI or designee becoming aware of the event using the pregnancy CRF and will be followed up for outcome.

11.6 Deaths

All deaths must be recorded on the notification of death CRF and sent to the CTRU within 5 working days of the site research team becoming aware of the death.

11.7 Overdose Definition and Reporting

11.7.1 Amitriptyline

In the event of an overdose (>200mg [20 tablets] ingested in one day), amitriptyline should be discontinued, and the participant should be observed closely for signs of toxicity. Appropriate supportive treatment should be provided if clinically indicated. Additionally, in the event of

any deliberate overdose (however small), all study medication should be stopped and the participant should be reviewed for suicidal ideation. The participant should be withdrawn from trial treatment, and assessed by the PI for consideration as to whether ongoing data collection (completion of participant questionnaires) is appropriate.

Overdose is considered an IME and should be reported as a SAE.

11.7.2 Ondansetron

In the unlikely event of overdose (>120mg ingested in one day), ondansetron should be discontinued, and the patient should be observed closely for signs of toxicity. Appropriate supportive treatment should be provided, if clinically indicated.

If an AE(s) is associated with ("results from") the overdose, the AE(s) should be recorded as a SAE, even if no other seriousness criteria are met.

11.7.3 Loperamide

In the unlikely event of overdose (>16mg ingested in one day), loperamide should be discontinued, and the patient should be observed closely for signs of toxicity. Appropriate supportive treatment should be provided, if clinically indicated.

If an AE(s) is associated with ("results from") the overdose, the AE(s) should be recorded as a SAE, even if no other seriousness criteria are met.

